3.1 General Study Design and Plan

This is a two arms randomized controlled multi-centre, parallel-group, double-blinded trial. The control group is a placebo and the treated group is Empagliflozin. The aim of the trial is to show superiority of Empagliflozin over placebo. Randomization was carried out by stratifying according to site, T2DM status and sex.

3.2 Inclusion-Exclusion Criteria and General Study Population

3.2.1 Inclusion criteria

- 1. Myocardial infarction with evidence of significant myocardial necrosis defined as a rise in creatinine kinase >800 U/l and a troponin T-level (or troponin I-level) >10x ULN. In addition, at least 1 of the following criteria must be the met:
 - Symptoms of ischemia.
 - ECG changes indicative of new ischemia (new ST-T changes or new LBBB).
 - Imaging evidence of new regional wall motion abnormality.
- 2.18 80 years of age.
- 3. Informed consent has to be given in written form.
- 4. eGFR > 45 ml/min/1.73m2.
- 5. Blood pressure before first drug dosing: systolic blood pressure>110mmHg.
- 6. Blood pressure before first drug dosing: diastolic blood pressure>70mmHg.
- 7. First intake of study medication ≤72h after myocardial infarction after performance of a

coronary angiography.

3.2.2 Exclusion criteria

- 1. Any other form of diabetes mellitus than type 2 diabetes mellitus, history of diabetic ketoacidosis.
- 2. Blood pH < 7,32.
- 3. Known allergy to SGLT-2 inhibitors.
- 4. Haemodynamic instability as defined by intravenous administration of catecholamine, calciumsensitizers or phosphodiesterase inhibitors.
- 5. >1 episode of severe hypoglycaemia within the last 6 months under treatment with insulin or sulfonylurea.
- Females of child bearing potential without adequate contraceptive methods (i.e. sterilisation, intrauterine device, vasectomised partner; or medical history of hysterectomy).
- 7. Acute symptomatic urinary tract infection (UTI) or genital infection.
- 8. Patients currently being treated with any SGLT-2 inhibitor (dapagliflozin, canagliflozin, empagliflozin) or having received treatment with any SGLT-2 inhibitor within the 4 weeks prior to the screening visit.

3.3 Randomization and Blinding

After screening, all eligible patients for the trial were randomized into one of the two arms of the study via Randomiser Software (Institute for Medical Informatics, Statistics and Documentation, Medical University of Graz, http://www.randomizer.at), which is programmed with a randomisation schedule provided by an independent statistician. The randomization was stratified by site, T2DM and by sex. Only the subject number and subject initials were recorded in the case report form (CRF). The investigator maintains a personal subject identification list (subject numbers with the corresponding subject names) to enable records to be identified.

Blinding of the medication was done by the pharmacy at the University Hospital in Salzburg, Austria. The pharmacy received the randomization list from the Institute for Medical Informatics, Statistics and Documentation at the Medical University of Graz, Austria by the independent statistician. The pharmacy distributed then the blinded medication to the study sites. The independent statistician and the pharmacists are otherwise not involved in the EMMY trial.

3.4 Study Assessments

Data are collected according to the following schedule:

	Visit 1 (V1) Screening / Baseline	Visit 2 (V2) (week 6 ± 2)	Visit 3 (V3) (week 12 ± 2)	Visit 4 (V4) (Week 26 ± 2)	Visit 5 (V5) (4 weeks ±1w after V4)
Informed Consent	X				
Inclusion/exclusion criteria	x				
Randomisation	x				
Demography, medical history	x			6.	
Concomitant medication	X	x	X	×	
Vital signs	x	x	x	x	
Height	х		0	OX	000
Weight	x	x	x	x	6
Physical examination	x	x	.00	x	
ECG	X			7	
Cardiac ultrasound	x	x		x	
Biobank sampling	x	x		×	
nt-proBNP (local)	x	x	x	x	
Blood sampling	X	x	x	x	
Liver function parameters (AST, ALT, GGT)	x	×	X	x	
Renal function parameters (creatinine, eGFR)	X	x	x	X	
Adverse Events	1 10	X	X	X	X
Dispense medication	X				
Drug accountability				X	
Safety assessment before discharge	×		V.		

4 Sample Size

Previous data showed that NT-proBNP levels decrease by about 50% within 6 months after acute myocardial infarction. To detect a relative 40% larger reduction in NT-proBNP levels

in the Empagliflozin group as compared to the placebo group with a power of 80% and an alpha-level of 0.05%, and assuming a correlation for NT-proBNP levels of 0.85, a sample size of 216 subjects in each group is necessary. To account for a dropout rate of about 10% each group will consist of 238 patients. A detailed document regarding power and sample size calculation is annexed to this SAP.

5 General Analysis Considerations

5.1 Timing of Analyses

The trial will end after the last subject has completed the follow-up telephone assessment (Study visit 5). All patients will be reviewed by a clinician at their last study visit in order to arrange return to appropriate routine clinical care pathways. The data analysis will be performed on data transferred to the file data_emmy_YYMMDD, having been documented as meeting the cleaning and approval requirements and after the finalization and approval of this SAP document.

5.2 Analysis Populations

5.2.1 Intention to Treat Population (ITT)

The ITT population includes all patients who were randomized and received at least one dose of the study medication (i.e. Empagliflozin or Placebo). The ITT population will be used for the primary efficacy analysis.

5.2.2 Per Protocol Population (PP)

The PP population will include all patients in the ITT population who completed week 26 evaluation without any major protocol violations. More specifically, the PP population will include all patients in the ITT population excluding:

- a- Patients not fulfilling inclusion/exclusion criteria at baseline, which was identified after randomization and first treatment dosing but who remained in the trial as no safety concern was considered by the principal investigators.
- b- Patients who did not complete week 26 evaluation
- c- Patients who took study medication for less than 75% of the study duration (study

duration = 26 + /- 2 weeks)

The list of potentially important protocol deviations will be identified, reviewed, and finalized prior to the release of the database.

5.2.3 Safety Population

All patients who were randomized and received at least one confirmed dose of study medication (i.e. Empagliflozin or Placebo) and provided any post-baseline safety information.

5.3 Covariates and Subgroups

5.3.1 Data transformation

Data might be transformed on a logarithmic scale in case of non-normality distribution.

5.3.2 Covariates adjustment

All analyses, including the primary analysis, will be adjusted for the variables used when stratifying the randomization. These variables are Sex and T2DM status. We will not be able to adjust for the variable centre as this might introduce too many categories. Analysis will also be adjusted for baseline levels of the dependent variables.

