#### 3. STUDY DESCRIPTION

#### 3.1 Design

This is a randomized, double-blind (patients and physicians), placebo controlled multi-center study to evaluate the effect of Empagliflozin 10mg once daily (p.o.) for 26 weeks on cardiac function and biomarkers for heart failure in patients with acute myocardial infarction (Figure 1). The study will be conducted in 11 sites in Austria (Appendix B) with an aim to enrol 476 patients (Figure 2) to evaluate the overall study hypothesis.

[figure not shown]

Figure 2 Study Flow Chart

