5.3.4 Multi-centre Studies

Because this study was not designed to detect centre effects with specific power, all centres will be grouped and analyses will be carried out as a whole. However, we will perform an exploratory analysis for centre effects with respect to each of the dependent variables. Qualitative and/or quantitative treatment-by-centre interactions will be investigated in this case. For the purpose of analysis, a small site will be defined as a site with < 4 ITT subjects in either treatment arm. Small sites will be ranked in descending order based on the total number of ITT subjects of the sites. The first small site will be pooled with the next small site, or with more sites if needed, until the pooled site/analysis centre has at least 4 ITT subjects in both the arms. The algorithm will continue down the list, and if the last few small sites are pooled but fail to be adequately large, they will be combined with the previously pooled smallest site/analysis centre.

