5.6 Multiple Testing

There is no need to control for the overall type 1 error using a multiple testing procedure since there is only one single primary efficacy endpoint.

6 Summary of Study Data

[figure not shown]
All summary tables will be structured with columns for each treatment and overall in the order (Overall, Placebo, Empagliflozin) and will be annotated with the total population size relevant to that table, including any missing observations. All continuous variables will be summarized using the following descriptive statistics: n (non-missing sample size), mean, standard deviation. The frequency and percentages (based on the non-missing sample size) of observed levels will be reported for all categorical variables. Demographic and clinical characteristics to be summarized will include all baseline variables. P-values will be added to compare baseline characteristics between Placebo and Empagliflozin groups.

Summary tables will be provided overall and also, if adequate, stratified according to: variables used in stratifying the randomization (i.e. Sex, T2DM status and Site), variables used in the subgroup analysis, and by visit.

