7.1 Primary Efficacy Analysis

The primary efficacy endpoint is the change in NT-proBNP from baseline to week 26. This primary endpoint will be analysed on the ITT population using a linear mixed effect model (LMEM) where the dependent variable is the NT-proBNP and the fixed effects are treatment, visit, treatment by visit interaction, the stratification factors Sex and T2DM and the level of NT-proBNP at baseline. The random effect component will include patients and unstructured covariance will be assumed for the within-subject errors. In case of non-convergence problems other covariance structures, such as compound symmetry, will be applied until the problem is resolved.

In this analysis, no missing data will be imputed. It will be handled by using the LMEM which assumes the data to be missing at random (MAR process). At week 26, estimates of mean values, the mean differences between the treatment groups and the associated 2-sided 95% confidence interval will be derived from the LMEM model through the use of estimated marginal means (or LS-means).

To claim superiority of Empagliflozin over Placebo, this primary efficacy analysis must show a statistically significant effect of treatment at an alpha level of 5% and two-sided test direction.

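### Site stratifies the randomisation but is left out of every efficacy model, and with 11 sites the reason given does not hold

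*SAP*

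**What the plan says.** SAP 3.1 states: "Randomization was carried out by stratifying according to site, T2DM status and sex". SAP 3.3 and Protocol 5.2 give the same three factors, and SAP section 6 (Summary of Study Data) again names the "variables used in stratifying the randomization (i.e. Sex, T2DM status and Site".

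SAP 5.3.2 sets the rule: "All analyses, including the primary analysis, will be adjusted for the variables used when stratifying the randomization". It then lists only sex and T2DM status and explains the gap: "We will not be able to adjust for the variable centre as this might introduce too many categories".

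The primary mixed model in SAP 7.1 follows that shorter list. Besides treatment, visit and their interaction, its fixed effects are "the stratification factors Sex and T2DM and the level of NT-proBNP at baseline". Secondary efficacy analyses I and II reuse this model. Analyses III and IV are regressions on treatment, sex, T2DM and baseline. None has a site term.

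On the number of centres, Protocol 3.1 says: "The study will be conducted in 11 sites in Austria". SAP 5.3.4 pools small sites "until the pooled site/analysis centre has at least 4 ITT subjects in both the arms", and adds: "we will perform an exploratory analysis for centre effects with respect to each of the dependent variables". That exploratory work includes treatment-by-centre interaction.

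**The concern.** There are two problems. First, SAP 5.3.2 contradicts itself. It cannot adjust for all stratification variables and also leave one out, and section 6 of the same document counts site among them.

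Second, the reason for leaving site out does not fit the trial's own figures. Eleven categories are few for a trial of this size, and the SAP elsewhere plans a larger centre model.

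Stratifying by site balances the arms within site, so between-site variation largely cancels from the treatment difference. A model without site leaves that variation in the residual, and the reported standard error is then larger than the true one. At stake is a slightly conservative test and a little lost power in a trial planned at only 80%. Bias and false-positive inflation are not at stake.

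**Working it through.** **Inputs.** 11 sites (Protocol 3.1). 216 evaluable per arm, 238 randomised per arm, 80% power, correlation 0.85, 40% larger reduction (Protocol 7.1). Two-sided 5% (Protocol 7.2, SAP 7.1). Quartile-based means and SDs from Protocol Appendix A. The site share of residual variance after covariates, ρ, is not in the documents; 0 to 10% is assumed.

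**The plan's own figure.** Δ = 0.4 × (653.67 − 282.67) = 148.4. With m = 0.1404, the SD of change is 772.98 × √(1 + m − 2 × 0.85 × √m) = 548.5. Then n = 2 × [(1.960 + 0.842) × 548.5 / 148.4]² = 214.4, so 215 per arm, against 216 stated. With the t distribution, power at 216 per arm is 80.1%. The figure reproduces.

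**Cost of site if it predicts nothing.** A week-26 linear model with intercept, treatment, sex, T2DM and baseline has 5 parameters; 10 site terms make 15. Error degrees of freedom go from 432 − 5 = 427 to 432 − 15 = 417. Noncentral-t power at 216 per arm is 80.11% both ways. The average is 432/11 = 39 evaluable patients per site (476/11 = 43 randomised).

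**Size of the centre models.** A site main effect needs 10 parameters. Adding treatment-by-centre interaction, as SAP 5.3.4 intends, needs up to 10 + 10 = 20.

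**Effect of omission, analytic.** Under perfect balance within site, the reported standard error is too large by 1/√(1 − ρ). The true alpha is 2 × [1 − Φ(1.966/√(1 − ρ))].

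| ρ | SE factor | True alpha, no site | Power, no site | Power, with site |
|---|---|---|---|---|
| 2% | 1.010 | 4.7% | 80.4% | 80.9% |
| 5% | 1.026 | 4.4% | 80.7% | 82.1% |
| 10% | 1.054 | 3.8% | 81.4% | 84.1% |

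**Effect of omission, simulated.** There were 8000 trials per cell with 476 randomised. Assumed:
- site sizes 133, 76, 57, 48, 38, 33, 29, 24, 19, 12 and 7
- blocks of 4 within site × T2DM × sex
- T2DM share 150/476 (target in Protocol section 4) and 20% in the smaller sex stratum
- random loss to 432, and an effect set for 80% power

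A week-26 linear model stands in for the mixed model. The SAP 5.3.4 pooling rule left 10 analysis centres (9 degrees of freedom).

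| ρ | Alpha, without / with site | Power, without / with site | Paired power gain (points) | Reported SE ÷ true SD, without site |
|---|---|---|---|---|
| 0% | 5.1% / 5.2% | 79.7% / 79.6% | −0.05 | 0.997 |
| 2% | 4.8% / 5.0% | 80.5% / 80.8% | 0.34 | 1.006 |
| 5% | 4.5% / 5.2% | 78.9% / 80.2% | 1.35 | 1.013 |
| 10% | 3.9% / 4.7% | 79.7% / 82.2% | 2.55 | 1.039 |

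The Monte Carlo standard error is about 0.24 points for alpha and 0.14 to 0.22 for the paired gain. Bias was within 0.002 in every cell. At ρ = 10% the true SD of the estimate was 0.0927 without site and 0.0923 with it.

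A separate simulation (6000 trials per cell, unpooled sites) gave power gains of −0.1, 0.5, 0.7 and 2.3 points at the same four shares.

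**The case against.** The case for leaving the plan alone has real content.

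- **The choice is disclosed and centre is not ignored.** SAP 5.3.4 adds that the study was not powered for centre effects, and plans an exploratory analysis. But adjusting for a stratification factor does not require power to detect it, and 5.3.4 does not commit to reporting a site-adjusted treatment effect.
- **The harm is small and in the safe direction.** This stands. The estimate is unbiased and its true spread hardly changes. The gain comes from a standard error that matches the design.
- **The residual site share may be small.** This stands for the primary endpoint. NT-proBNP is measured centrally (Protocol 5.5.6, SAP 8.3) and adjusted for baseline, and echo recordings are read centrally (Protocol Appendix C). What remains is the local-laboratory fallback for NT-proBNP, local HbA1c and local echo machines. At a 2% share the alpha difference is within simulation error, and nothing in the documents supports a share as high as 10%.
- **HbA1c is analysed only in known T2DM.** The target is 150, so about 150 × 0.9 = 135 evaluable. A rerun in that subset with unpooled sites (4000 trials per cell) found on average 4.6 of 11 sites with fewer than 4 patients in an arm. Power without and with site was 79.9% and 79.0% at a 0% share, 79.3% and 79.2% at 2%, and 80.5% and 80.5% at 5%. For this endpoint there is no gain at those shares and a cost of about 0.9 point at zero. Pooling must therefore be done on the subset analysed.
- **It may be too late.** The protocol synopsis gives database lock as 17 May 2022. This limits the remedy but does not remove the inconsistency.

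**Conclusion.** The concern holds. The wording of SAP 5.3.2 is inconsistent with SAP 3.1, 3.3 and section 6 whatever the size of any site effect, and the reason given for excluding site fails with 11 sites and about 432 evaluable patients.

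The practical consequence is modest and conditional: about 0.3 to 2.6 power points lost if site carries 2% to 10% of the residual variance, with a conservative test, and about 0.1 point or less to be paid in the primary analysis if it carries none. These sizes rest on assumed site shares, site sizes, block size and sex split, and on a single-visit simplification of the mixed model.

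This should be changed as a near-free improvement. It does not threaten the validity of a superiority claim.

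**What to change.** In SAP 5.3.2, replace the two sentences that list the variables and exclude centre with, for example: *The stratification variables are site (small sites pooled by the rule in Section 5.3.4), sex and T2DM status.*

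Add site to the primary model in SAP 7.1, to secondary efficacy analyses I to IV and to the models for continuous secondary endpoints. Fix the form in advance. A random intercept would also be valid, but fixed pooled centres add no covariance parameter and so do not add to the convergence difficulty that 7.1 anticipates. For HbA1c, apply the pooling rule to the T2DM patients actually analysed.

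If the data are already unblinded, leave the primary analysis as planned, report the site-adjusted model as a labelled sensitivity analysis, and state in 5.3.2 that only two of the three stratification factors were adjusted for.

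The cost is one reworded statement and one model term with at most 10 parameters or, after unblinding, one additional analysis.

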5.3.3 Subgroup analysis

Subgroup analyses will focus on the evidence for a difference in treatment effects using the interaction term. Subgroup-specific treatment effect estimates will be presented only if the interaction effect is judged to be statistically significant. Interaction effects will be investigated for the following variables:

- T2DM
- Previous cardiovascular events (myocardial infarction or stroke)
- Previous myocardial infarction
- History of heart failure
- Age
- Sex

- Renal function
- LV-EF
- Baseline levels of the dependent variable. Here the interaction will be investigated using
 the original dependent variable and/or by categorizing this dependent variable into a
 clinically relevant number of categories. Percentiles will be used if there are no prior
 clinical cut offs.

Forest plots will be produced to illustrate subgroup effects and interactions. If needed, three way interactions will also be included (e.g. to investigate the interaction between treatment, NT-proBNP and CK).

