#### Date: 17 October 2022

#### 5.2 Randomisation

After screening, all eligible patients for the trial will be randomised into one of the two arms of the study via Randomiser Software (Institute for Medical Informatics, Statistics and Documentation, Medical University of Graz, http://www.randomizer.at), which will be programmed with a randomisation schedule provided by an independent statistician. The randomisation will be stratified by site, type 2 diabetes and by sex.

Only the subject number and subject initials will be recorded in the case report form (CRF). The investigator will maintain a personal subject identification list (subject numbers with the corresponding subject names) to enable records to be identified.

A summary of all visits and procedures has been outlined below (Table 1). A more detailed description of each visit and accompanying procedures can be found later in the protocol (5.4 - 5.5)

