#### 7. STATISTICAL ANALYSES

#### 7.1 Sample size and power considerations

Previous data showed that nt-proBNP levels decrease by about 50% within 6 months after acute myocardial infarction. To detect a relative 40% larger reduction in nt-proBNP levels in the Empagliflozin group as compared to the placebo group with a power of 80% and an alpha-level of 0.05%, and assuming a correlation for nt-proBNP levels of 0.85, a sample size of 216 subjects in each group is necessary. To account for a dropout rate of about 10% each group will consist of 238 patients.

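### SAP 5.3.3 shows subgroup estimates only after a significant interaction, yet promises forest plots of subgroup effects without condition: the rules conflict, or display depends on the p-value

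*SAP*

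**What the plan says.** SAP 5.3.3 bases the subgroup analysis on interaction terms and lists nine factors, among them type 2 diabetes, sex, age, renal function, LV-EF and the baseline value of the outcome. It contains two display rules:

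- "Subgroup-specific treatment effect estimates will be presented only if the interaction effect is judged to be statistically significant".
- "Forest plots will be produced to illustrate subgroup effects and interactions".

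The second has no condition. Neither sentence refers to the other, and the section gives no separate significance level for interactions. The general level, two-sided 5%, is in Protocol 7.2, which otherwise leaves the subgroup analyses to the SAP.

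A rule for forming categories (clinical cut-offs first; then "Percentiles will be used if there are no prior" cut-offs) is attached only to the baseline value of the dependent variable.

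Diabetes has a special place in the design. Protocol 5.2: "The randomisation will be stratified by site, type 2 diabetes and by sex". Protocol section 4 sets a recruitment target of 150 patients with diabetes.

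**The concern.** A forest plot of subgroup effects is a display of subgroup-specific estimates. For a factor whose interaction is not significant, the first rule forbids what the second promises. The analyst has to choose, possibly after seeing the results.

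If the restrictive rule prevails, two things follow. A treatment effect that is consistent across diabetes status, which is a useful result for a stratification factor with its own recruitment target, would usually be reported only as a non-significant test, without model-based estimates and intervals. And the differences that do appear have been selected for being large, so on average they overstate the truth.

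A smaller point belongs to the same section. A forest plot needs categories, and none are defined for age or renal function, nor for LV-EF when another outcome is analysed. The interaction tests can use these as continuous variables; the plot cannot.

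**Working it through.** **Text.** For a factor with a non-significant interaction:

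| Reading | First rule | Forest plot | Result |
|---|---|---|---|
| Both literal | estimates not shown | estimates shown | conflict |
| Plot follows the first rule | not shown | not shown | display depends on p |
| First rule covers text and tables only | not shown there | shown | nothing lost, but the first sentence does not say this |

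**Size if the restrictive rule governs.** The SAP model adjusts for baseline (5.3.2: "Analysis will also be adjusted for baseline levels of the dependent variables"; 7.1 names "the stratification factors Sex and T2DM and the level of NT-proBNP at baseline"), so I use the baseline-adjusted SD, with a single-visit ANCOVA standing in for the mixed model at week 26.

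*Inputs.* From Protocol Appendix A: means 653.66 and 282.66; SDs 772.98 (baseline) and 289.60 (6 months); relative reduction 0.40. From Protocol 7.1: 216 analysed per arm, and the planning value, "assuming a correlation for nt-proBNP levels of 0.85". From Protocol section 4: 150 of 476 with diabetes, hence 326 without. My assumptions: correlations 0.5 and 0.3 as less favourable values, an interaction of half or all of the planned effect, and the 5% level for interactions.

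*The plan's own figure.* Planned effect = 0.4 × (653.66 − 282.66) = 148.4. Appendix A's change-score SD at correlation 0.85 is 548.5, giving n = 2 × (548.46 × (1.960 + 0.842)/148.4)² = 214.4, so 215 per arm against 216 stated. The inputs are therefore read correctly.

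*Formulas.* Adjusted SD = 289.60 × √(1 − r²). Overall SE = SD × √(2/216). Interaction SE = overall SE × √(476/150 + 476/326) = overall SE × 2.153. With z = interaction / interaction SE, the probability of withholding is Φ(1.96 − z) − Φ(−1.96 − z). Overstatement is E(|Z| given |Z| > 1.96)/z, where Z is normal with mean z and SD 1.

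| | r = 0.85 | r = 0.5 | r = 0.3 |
|---|---|---|---|
| Adjusted SD | 152.6 | 250.8 | 276.3 |
| Overall SE | 14.7 | 24.1 | 26.6 |
| Interaction SE | 31.6 | 51.9 | 57.2 |
| No interaction: withheld | 95% | 95% | 95% |
| Half effect (74.2): z | 2.35 | 1.43 | 1.30 |
| Half effect: withheld | 35% | 70% | 75% |
| Half effect: overstatement | 1.24 | 1.82 | 1.97 |
| Full effect (148.4): z | 4.70 | 2.86 | 2.59 |
| Full effect: withheld | 0.3% | 18% | 26% |
| Full effect: overstatement | 1.00 | 1.11 | 1.17 |

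A simulation of the ANCOVA with a treatment-by-diabetes term (3,000 trials per case, 432 analysed, 136 with diabetes) agreed: 36%, 73% and 75% withheld at half effect; 0.3%, 18% and 26% at full effect.

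*Fewer patients with diabetes, half effect.* With 100: 46% withheld (r = 0.85) and 79% (r = 0.3). With 60: 61% and 85%.

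*Precision of what is withheld.* Patients with diabetes per arm = 150 × (216/238)/2 = 68.1. The 95% CI half-width is 1.96 × SD × √(2/68.1) = 51.3 (r = 0.85) to 92.8 (r = 0.3), against a planned effect of 148.4.

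*Sensitivity to the SD.* With the unadjusted change-score SD of 548.5, the interaction SE is 113.6. A full-size interaction is then withheld in 74% of trials, and the half-width is about 184, wider than the planned effect. That SD does not match the SAP model, but it shows how far the figures depend on the variance.

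**The case against.** The strongest reply is that the first rule may govern text and tables only, while the unconditional plots show every factor. Nothing is then lost. There is some support for this: if the rule also covered the plots, then with no true interactions and nine tests treated as independent, 0.95⁹ = 63% of trials would have nothing to plot, which sits badly with a firm promise of plots. But the sentence limits presentation in general, and a forest plot presents these estimates. The reading is possible; the text does not establish it.

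Second, withholding estimates unless the interaction is significant guards against over-reading nine factors tested without multiplicity control. The aim is sound. The filter, however, passes exactly the factors with the most extreme differences: with no true interactions, 9 × 0.05 = 0.45 factors are expected to pass.

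Third, SAP section 6 plans summary tables by stratification and subgroup variables where adequate. A reader could form crude differences from them, but not the adjusted estimates.

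Fourth, the magnitudes depend on assumptions. This stands. The 95% is simply the complement of a 5% test; the rest varies with the correlation, the SD and the size of the interaction. It is also on the raw scale, while SAP 5.3.1 says: "Data might be transformed on a logarithmic scale in case of non-normality distribution". On the log scale only the 95% carries over directly.

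Last, when ejection fraction is the outcome, the existing category rule already covers LV-EF. That narrows the plotting gap but does not close it.

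**Conclusion.** The concern holds. The ambiguity in SAP 5.3.3 is certain; the loss of estimates occurs only if the restrictive sentence is applied to the plots. In that case the filter matters most for consistent effects and modest interactions, and hardly at all for a large interaction at the planned correlation. Under the baseline-adjusted model, the diabetes estimate it would hide is precise enough to inform.

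This is a reporting matter. The interaction tests are run either way, and SAP 7.2 rests superiority on the primary analysis alone. It should be corrected, but it does not threaten the trial's main result.

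**What to change.** Replace the restrictive sentence in SAP 5.3.3 with: *For every listed subgroup, the forest plot will show the treatment-effect estimate with its 95% confidence interval and the interaction p-value, whatever that p-value is; all of these analyses are exploratory.*

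Add one sentence extending the existing category rule (clinical cut-offs, otherwise percentiles) to age, renal function and LV-EF for plotting, with the cut-points fixed before unblinding. The interaction tests can stay continuous.

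The cost is one sentence replaced and one added; the models and plots are already planned. The downside is a little more output and some risk that readers make too much of exploratory estimates. The label and the interaction p-values beside them limit that risk.
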